Treatments. Subjects will initially receive 12 weeks of treatment with a single psychiatrist. The baseline treatment visit will last 45 minutes and subsequent visits 30 minutes. The first session will serve the following purposes: (1) confirm history; (2) obtain baseline ASAD symptoms; (3) provide explanatory framework for treatment; (4) address issues/concerns about medication; (5) describe specific side effects and characteristic medication response patterns; (6) establish a warm, empathic relationship, and engage the patient's trust; (7) explain the purpose and design of the study; and (8) make clear to the patient that the physician recognizes, understands and is familiar with ASAD. To ensure external validity, treating psychiatrists do not provide instructions about any exposure or cognitive therapy exercises. At the end of each visit pills will be provided as vilazodone 10 or 20 mg pills (depending on total dose), and matching placebo. A sufficient supply will be provided to last until the next visit (+/-3days), and unused medication will be collected from the patient at each visit. Brief ratings will be conducted by the psychiatrist to assess depression and adverse events, and vital signs will be assessed.

Dosage will initially be prescribed according to a fixed schedule, which may be modified in the case of nonresponse or intolerable side effects. It will start at 10mg/day and be increased to 20mg/day after 1 week and 40 mg/day after two weeks (optional). Patients without significant adverse effects who are not remitted (CGI-I=1) will have their dose increased to a maximum of 40 mg/day for the remainder of the study, if tolerated. Dosage can be held steady or lowered at any time during the study as clinically indicated in the event of adverse effects.

At the week visit 12 (or at premature termination), a complete medical workup (bloods, urine, EKG, physical exam) will be repeated. Participants at week 12 will be offered post-study open treatment and referrals, including the option of continuing on vilazodone if clinically appropriate. If discontinuation of study vilazodone is clinically indicated at any time, dosage will be tapered according to the following schedule, based on dose at endpoint:

Endpoint Dose Taper Schedule

40mg -->20mg for 4 days, 10mg for 7 days, then discontinue.

30mg	-->20mg for 4 days, 10 mg for 7 days, then discontinue
20mg	-->10 mg for 7 days, then discontinue.
10mg	--> discontinue

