Subjects will also complete a computer-based Attention Bias Measurement at baseline, week 1, and week 12 visits, using procedures developed by Bar Haim (2010). This will assess bias to look toward angry or neutral faces, as a predictor and correlate of treatment response.

The stimuli are face photographs of 20 different individuals, with an angry and a neutral expression for each individual. The protocol consists of 120 trials (80 angry-neutral and 40 neutral-neutral presentations). Each trial begins with a fixation cross “+” presented in the center of the monitor for 500 ms. Immediately following termination of the fixation cue, the computer presents two faces of the same individual, positioned vertically. Each pair of faces displays one of two combinations of emotions (i.e., neutral and angry, or neutral and neutral).

After presentation of the face pair for 500 ms, a probe (“<” or “>”) appears in the location of one of the faces. Participants are instructed to press the button (left or right, corresponding to the direction of the probe pointer).

The task takes 5-10 minutes to complete.

You can upload charts or diagrams if any

Criteria for Early Discontinuation

Criteria for Early Discontinuation

Adherence and termination of study treatments

Adherence -- Rules of the treatment protocol will be carefully explained to patients by intake screeners and in consent forms. Patients who miss study visits will be actively followed up by phone and mail. Serious protocol violations, such as use of proscribed outside treatments or substance abuse, will be reviewed by the PI and will result in withdrawal from the study treatment. Substance use will be assessed by initial drug screen and subsequent patient report. If clinical suspicion of substance use arises based on erratic behavior, alcohol on breath, and other signs and symptoms, spot toxicology screens will be used. Treating psychiatrists will monitor patient drinking behavior with repeated queries over the course of treatment. If patients are withdrawn from the study treatments, staff will make every effort to make this event constructive and empathic. Patients will continue to be assessed for the full **12** weeks of the study. A pill count will be conducted after each visit to assess adherence to medication schedule.

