Blind Treatment: Another risk is that participants will not be told whether they were assigned to vilazodone or placebo until completing the 14 week assessment period, except in the event of a medical emergency. This may delay or interfere with selection of optimal post-study treatments.

b. Risks Associated with Assessment Procedures:

Venipuncture: Mild discomfort and, rarely, a small arm bruise, clot or infection may occur at the site of the blood drawing.

Self-Report Measures, Assessor Ratings: Patients could develop mild to moderate emotional discomfort or frustration associated with psychiatric interviewing or filling out questionnaires.

Describe procedures for minimizing risks

To minimize treatment risks, patients will be screened for conditions that significantly increase risks of treatment, adverse effects and vital signs will be monitored at every visit, and dosing is flexible to allow reductions in the event of adverse effects. Patients will be educated about potential adverse interactions with other medications they may wish to take and advised to contact study physicians before starting new medications. Patients will be informed that they may withdraw from study treatment at any time.

Randomization codes will be broken for patients upon their termination from the study, or earlier in the event of a medical emergency.

Venipuncture will be conducted with standard safety procedures.

Self-Report Measures, Assessor Ratings: Study clinicians are skilled at dealing with distress and will make efforts to help clients to feel as comfortable as possible (e.g., by giving breaks during an evaluation, offering encouragement).

Methods to Protect Confidentiality

Describe methods to protect confidentiality

All data with identifying information will be stored in locked file cabinets or password-protected computer files. Data being analyzed will be identified by subject codes and identifying information will be removed. The identity of patients will not be revealed in the presentation or publication of any results from the project. All assistants and others working on the project will be educated about the importance of strictly respecting patients' rights to confidentiality.

Will the study be conducted under a certificate of confidentiality?

No

Direct Benefits to Subjects

Direct Benefits to Subjects

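### Could the protocol's two end-of-blind statements let a patient's code be broken before that patient's last ratings?

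*Protocol*

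**What the plan says.** Two sentences in the protocol's risk section fix the end of the blind. Under Describe procedures for minimizing risks: "Randomization codes will be broken for patients upon their termination from the study, or earlier in the event of a medical emergency". Under Blind Treatment, participants are not told their assignment "until completing the 14 week assessment period", again with a medical-emergency exception.

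Other sections bear on how these are read:

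- Describe procedures for minimizing risks, just before the code-break sentence: "Patients will be informed that they may withdraw from study treatment at any time".
- Criteria for Early Discontinuation, under the heading "Adherence and termination of study treatments", on patients withdrawn from study treatments: "Patients will continue to be assessed for the full" 12 weeks.
- Study Procedures: "At the week visit 12 (or at premature termination), a complete medical workup" is repeated, and "Participants at week 12 will be offered post-study open treatment and referrals, including the option of continuing on vilazodone if clinically appropriate".
- Compensation and/or Reimbursement: eight visits are paid over 12 weeks, whether or not the patient is still on study treatment.

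The SAP does not mention blinding or code breaks.

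**The concern.** The two sentences appear to give different dates. A completer finishes at week 12, where the first sentence would open the code, yet the second keeps it closed until week 14. No 14-week period appears elsewhere in the text reviewed.

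The more serious worry is the word termination. The heading in Criteria for Early Discontinuation applies it to treatment, and Study Procedures speaks of premature termination without saying from what. If a code were opened when a patient stopped drug, that patient's remaining ratings to week 12 would be unblinded.

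That would matter here. Many outcomes are self-rated, and in Study Procedures "Brief ratings will be conducted by the psychiatrist to assess depression and adverse events", so the treating clinician is also a rater. The SAP fits time as an additive factor with no group-by-time term. The group contrast therefore pools visits, and any rating made after a code break would enter it. With 40 patients randomised and a 50% chance of placebo, one patient is about 1/20 = 5% of an arm.

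**Working it through.** No statistical figure is at issue. The check is arithmetic on durations, followed by a comparison of wording.

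**1. Is 14 weeks derivable?**

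- Paid schedule: 6 × $30 + 2 × $60 = $300, the stated maximum over 12 weeks. This leaves no paid week-14 visit. Gap: 14 − 12 = 2 weeks.
- Week 12 plus the longest listed taper: 4 + 7 = 11 days, so 12 + 11/7 = 13.57 weeks. This is close to 14, but no assessment is tied to the taper.
- A 2-week washout plus 12 weeks of treatment gives 14, but washout applies only to some patients and precedes the pretreatment assessment.
- The 17-week maximum delay does not settle the matter. It is reached as 5 + 12 = 17 or as 1 + 4 + 12 = 17, while one week of assessment with a 5-week washout gives 1 + 5 + 12 = 18.

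The text supports no route to 14, so a slip for 12 is the likeliest explanation.

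**2. What does termination from the study mean?**

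- The sentence immediately before the code-break rule concerns withdrawal from study *treatment*. The code-break rule concerns termination from the *study*. The contrast is between neighbouring sentences.
- Criteria for Early Discontinuation and the compensation section use study treatment when they mean stopping drug, and both keep such patients under assessment. These patients have not left the study.
- The heading that uses termination names study treatments explicitly, so it does not blur the distinction. The premature-termination phrase triggers a medical workup, not a code break.

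**3. Who could be unblinded before a rating (emergencies aside)?**

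| Patient | Code opens (literal reading) | Ratings still to come |
|---|---|---|
| Completer | End of study, week 12 or later | 0 |
| Stops drug, stays in assessment | End of assessment, week 12 or later | 0 |
| Leaves all assessment at week w < 12 | Week w | 0, as none is collected after leaving |

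The Blind Treatment sentence gives patients a second safeguard. Whether the period is 12 or 14 weeks, the assignment is disclosed only after assessment is complete.

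**4. The loose reading, for comparison.** Suppose termination meant stopping drug, and assume visit 1 is week 0 and visit 8 is week 12 (the text reviewed does not give visit weeks). Then between 8 − 7 = 1 and 8 − 1 = 7 paid visits of an early stopper would follow the code break. The documents give neither a stopping rate nor an effect of unblinding on ratings, so no bias can be calculated.

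**The case for a change.** The best case for a change is that no sentence expressly keeps the code closed to raters until the week-12 ratings are done. The Blind Treatment sentence covers only what participants are told. Early stopping is foreseeable: the protocol lists three routes to removal from treatment and allows withdrawal from treatment at any time. The treating psychiatrist rates some outcomes, and a clarifying phrase would cost almost nothing. The SAP is also silent on ratings made after an emergency code break, which the protocol does permit.

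Some of this stands. The term is undefined, the rater side is left to inference, and the week numbers disagree. But the inference is short, because the code-break rule is tied to leaving the study and treatment-withdrawn patients have not left it. The SAP's silence on emergency code breaks is a common omission. An analyst would flag any such rating and check the result without it. The additive time term does not create the problem, since any repeated-measures model would include those ratings and a week-12 contrast would give late ones more weight. Offering open treatment at week 12 before the assignment is known is not a contradiction either: the protocol itself lists delayed or hampered choice of post-study treatment as a risk of the blind.

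**Conclusion.** No change to the plan follows. The 14-week figure is 2 weeks longer than the 12-week schedule stated elsewhere and is most likely a clerical slip; it could only lengthen the blind, not shorten it. The missing definition is a gap that trial staff would fill sensibly, because the surrounding text already separates stopping treatment from leaving the study. Read literally, 0 ratings follow a non-emergency code break, and no bias is shown.

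This rests on termination from the study meaning the end of a patient's assessments, and on the text available for review, which contains no visit-week table. The 12- and 14-week statements should be reconciled as an editorial matter if the document is next revised. Nothing in the design, the estimate or its interpretation depends on that.

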Data Analysis Plan for IRB #6856: Vilazodone in Separation Anxiety Disorder

Aggregate statistics for demographic and clinical characteristics of the two groups were calculated and compared using chi-square tests and t-tests, as appropriate. All quantitative post-randomization outcomes were graphed and their distribution assessed for outlier values. To compare outcomes in the two groups, mixed effect logistic regression was used for the categorical outcomes and mixed effect regression models for quantitative outcomes, with subject-specific random effects and a first order auto-correlation structure for observations within the same individual. Time was included in the model as an additive factor (due to relatively low sample size, we did not test for differential time effect through interaction with group).

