Specify subject population

adults with separation anxiety disorder

Number of completers required to accomplish study aims

40 randomized

Projected number of subjects who will be enrolled to obtain required number of completers

50

Age range of subject population

18-60

Gender, Racial and Ethnic Breakdown

We anticipate randomizing 30 women and 10 men; 20 Hispanics and 20 non-Hispanics; 27 whites, 10 African-Americans, and 3 Asians.

Description of subject population

Men and women, of any race and ethnicity, who present for treatment of DSM5 ASAD at the Anxiety Disorders Clinic of the New York State Psychiatric Institute.

Recruitment Procedures

Describe settings where recruitment will occur

Anxiety Disorders Clinic

How and by whom will subjects be approached and/or recruited?

Subjects who respond to treatment notices will be screened on the phone by a research assistant. After psychiatric assessment, the assessing psychiatrist will invite eligible subjects to participate in the study.

How will the study be advertised/publicized?

Patients will be obtained through: (a) word-of-mouth referrals from former patients, (b) referral from area medical and mental health professionals, (c) publicity about the study, including articles in local newspapers and magazines, appearances on local radio and television shows, etc., leading to self-referral of prospective patients, (d) recruitment notices placed in local media and on the internet (i.e. Facebook and Twitter), (e) Columbia Recruit Me, (f) Radio audio ads

Do you have ads/recruitment material requiring review at this time?

Yes

Does this study involve a clinical trial?

Yes

Please provide the NCT Registration Number

NCT01999920

Concurrent Research Studies

Will subjects in this study participate in or be recruited from other studies?

Yes

Describe concurrent research involvement

From the Anxiety Disorders Clinic psychiatric screening evaluation protocol (IRB #5029)

Inclusion/Exclusion Criteria

Name the subject group/sub sample

Adult Separation Anxiety Disorder patients

Create or insert table to describe the inclusion criteria and methods to ascertain them

Inclusion criteria:

Method of Ascertainment

1. Males or females between the ages of 18 and 60 History

2. Current primary (most clinically significant) diagnosis of DSM5 ASAD

SCID-I, Clinical Interview for ASAD

3. Able to give consent, fluent in English.

Clinical Interview

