Patients with inadequate response (persistent diagnosis of ASAD and meeting other inclusion/exclusion criteria) to current medication will be evaluated to ascertain that they are receiving the appropriate dose of that medication. They will be asked for consent to contact their prescribing doctor. After consultation with the pre-study prescribing doctor (if patient consented to contact), patients will be brought up to the maximal appropriate dose before determining their eligibility for this study. For patients who remain inadequately responsive after an adequate trial of their current medication, after the patient consents to participate in this study, the patient will be instructed on how to taper medication as clinically indicated to minimize discontinuation-related adverse effects. A study psychiatrist will see the patient weekly during this period **and complete a CGI-change scale -- a score of 6, much worse, or greater will trigger additional clinical assessment and prompt a discussion about continued participation.** Such subjects will discontinue prohibited medication for > 2 weeks, or 5 half-lives (whichever is longer), (and 5 weeks for fluoxetine), before proceeding with the pretreatment assessment. Patients with inadequate response to vilazodone will be excluded. Patients will not be withdrawn from effective treatment for the purpose of entering this study.

Indicate which of the following are employed as a part of screening or main study consent procedures

Consent Form

Persons designated to discuss and document consent

Select the names of persons designated to obtain consent/assent

[name]

[name]

Type in the name(s) not found in the above list

Study Procedures

Describe the procedures required for this study

Week 0 Baseline Visit. Randomization and Pretreatment Assessment Subjects will be randomized to vilazodone or placebo by a computer-generated random-number program, with treatment assignment sealed in opaque envelopes. Randomization sequences will be provided by the study statistician, who has no contact with study subjects.

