Criteria for removal from study treatment, including non-adherence. These will be defined as follows: a) patients who deteriorate in treatment, as defined during weeks 0-12 by CGI-I score > 5 and remain similarly impaired at re-assessment one week later; b) patients who commit serious violations of the protocol; and c)

patients who miss more than 3 consecutive days of medication or a total of 12 days within weeks 0-12. Patients who are non-adherent with a clinic visit will be contacted by the investigator to elucidate reasons for non-adherence.

Blood and other Biological Samples

Please create or insert a table describing the proposed collection of blood or other biological specimens

Prior to study entry, and at the week 12 visit, **25ml** of blood will be drawn for: **oxytocin levels**, CBC, chemistry, thyroid tests, and in women, pregnancy test. Urine will be obtained for drug screen and urinalysis.

Assessment Instruments

Create a table or give a brief description of the instruments that will be used for assessment

(1 hour) Structured Clinical Interview for DSM IV (SCID-I) (First et al., 2002), used to determine Axis I disorders

(10 min) Structured Clinical Interview for Separation Anxiety Disorder (Cyranowski et al., 2002), modified for DSM-5. The eight separation anxiety disorder criteria are rated for both childhood (rated at baseline only) and past week time frames, scored as 0 (not at all), 1 (sometimes), 2 (often) or ? (don't recall). In keeping with the DSM-5 guidelines, endorsement of three or more of the eight criterion symptoms (symptoms rated as '2' or 'often') is used as a threshold to determine categorical (yes/no) diagnosis of separation anxiety disorder. Scores on each of the eight items are also summed to produce a continuous measure of separation anxiety symptoms experienced during childhood and adulthood (range for each scale=0–16).

(10 min) Hamilton Rating Scale for Depression (Hamilton, 1960) This standard scale will be used to assess severity of depression.

(10 min) Quality of Life Enjoyment & Satisfaction Questionnaire (Q-LES-Q, Endicott et al, 1993): self-rated assessment of quality of life.

(5 min) Arizona Sexual Experiences Scale (ASEX) (McGahuey et al., 2000): will be used to assess sexual functioning as a self-rating. It is a five-time rating scale and has been shown to have adequate internal consistency, test-retest reliability, and convergent and discriminant validity.

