The potential direct benefit to patients who enter this study will be to obtain relief from ASAD symptoms to improve their quality of life. Vilazodone is an SSRI, and SSRIs have appeared efficacious for childhood separation anxiety disorder. Also, Vilazodone is FDA-approved for the treatment of depression, and it may be helpful for comorbid symptoms of depression in ASAD.

Compensation and/or Reimbursement

Will compensation or reimbursement for expenses be offered to subjects?

Yes

Please describe and indicate total amount and schedule of payment(s).

Include justification for compensation amounts and indicate if there are bonus payments.

Participants will receive \$30/evaluation for completing each visit 2,3,4,5,6, and 7; \$60/evaluation for completing each visit 1 and 8, to be paid by cash after each visit (maximum total of \$300 over the 12 weeks of the study).

Subjects will be paid for each of these assessments that are completed at the specified week, regardless of whether they are continuing on study treatment or not.

Uploads

Upload the entire grant application(s)

Upload copy(ies) of unbolted Consent Form(s)

CF unbolted 9.30.16.pdf

Upload copy(ies) of bolded Consent Form(s)

CF bolded 9.30.16.pdf

Upload copy(ies) of recruitment materials/ads to be reviewed

ads sep anxiety revision 1.pdf

ASAD ad 9.6.16.pdf

Sep_Anx_Ad_pull_tabs.pdf

Sep_Anx_Ad_loved_one.pdf

Vilaz_Paid_Craigslist_Posting_.pdf

Sep Anx Ad partner or spouse (no stamp).pdf

Sep Anx Ad child (no stamp).pdf

Upload copy(ies) of the HIPAA form

HIPAA_09.06.16.pdf

Upload any additional documents that may be related to this study

Continuation_memo.approved_pending.09.30.16.pdf

References

References

Bar-Haim Y. Research review: Attention bias modification (ABM): a novel treatment for anxiety disorders. J Child Psychol Psychiatry. 2010 Aug;51(8):859-70.

Cyranowski JM, Shear MK, Rucci P, Fagiolini A, Frank E, Grochocinski VJ, et al. Adult separation anxiety: psychometric properties of a new structured clinical interview. Journal of psychiatric research.36:77-86.

2002 Gabbard G. (ed.) Gabbard's Treatments of Psychiatric Disorders, 5th Edition. American Psychiatric Publishing Inc, Washington, DC, In Press

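### The SAP's model for quantitative outcomes contains no baseline-severity term, so a trial of about 20 per arm gives up precision that an already scored baseline could recover

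*SAP*

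**What the plan says.** The SAP (Data Analysis Plan for IRB #6856) is one paragraph. For quantitative outcomes it gives mixed effect regression "with subject-specific random effects and a first order auto-correlation structure for observations within the same individual". The only other model term it describes is time: "Time was included in the model as an additive factor", with no group-by-time interaction because the sample is small. Pre-treatment data appear only in a comparison of demographic and clinical characteristics by chi-square and t-tests. The outcome values it mentions are post-randomization values.

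The protocol does provide a scored baseline for at least one measure. Under Assessment Instruments, for the separation-anxiety interview, "The eight separation anxiety disorder criteria are rated for both childhood (rated at baseline only) and past week time frames". Also, "Scores on each of the eight items are also summed to produce a continuous measure of separation anxiety symptoms experienced during childhood and adulthood", each total running from 0 to 16. Under Study Procedures, the first session includes obtaining baseline symptoms.

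The planned sample is "40 randomized" (Description of Subject Population). On allocation, Study Procedures says "Subjects will be randomized to vilazodone or placebo by a computer-generated random-number program", with no stratification by severity stated.

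**The concern.** A random intercept and AR(1) errors describe how one person's measurements go together. They do not remove between-person variance from the standard error of the arm contrast; a pre-treatment predictor in the model does that. Testing characteristics between arms does not do it either.

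No bias is at stake. The unadjusted contrast is unbiased over randomizations, and its standard error already allows for chance imbalance. What is at stake is precision, in a trial whose own SAP calls the sample low. There is a second cost: with no stated rule, whether and how baseline enters the model can be settled after the data are seen.

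**Working it through.** Neither document gives a power calculation, so there is no stated figure to reproduce.

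**Inputs from the documents**
- 40 randomized, with a 50% chance of placebo (Risks section), so about 20 per arm.
- Random effects, AR(1) and additive time (SAP).
- Eight paid visits. The protocol's payment clause covers each "evaluation for completing each visit 2,3,4,5,6, and 7", plus visits 1 and 8. I read this as one baseline and up to seven post-baseline visits.

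**Assumptions, because the documents are silent**
- Two-sided 0.05, 80% power, outcome SD = 1.
- Baseline-outcome correlation r from 0 to 0.7.
- For repeated measures: random-intercept share (icc) 0.3 or 0.5, AR(1) parameter (phi) 0.3 or 0.6, equally spaced visits, no dropout.

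**Chance imbalance.** The SE of the baseline mean difference is sqrt(2/20) = 0.316 SD. P(|difference| > 0.5 SD) = 2 × [1 − Φ(0.5/0.316)] = 0.114.

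**Single visit.** Adjustment multiplies the variance by (1 − r²) × (1 + 1/36), the second term being the cost of estimating one slope with 40 patients. Detectable effects use the noncentral t, with 38 df unadjusted and 37 df adjusted. The multiplier on the SE is about 2.88 in both.

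| r | variance factor | detectable effect (SD) | equivalent unadjusted N = 40/factor |
|---|---|---|---|
| unadjusted | 1 | 0.909 | 40 |
| 0 | 1.028 | 0.922 | 38.9 |
| 0.2 | 0.987 | 0.904 | 40.5 |
| 0.3 | 0.935 | 0.880 | 42.8 |
| 0.5 | 0.771 | 0.799 | 51.9 |
| 0.7 | 0.524 | 0.659 | 76.3 |

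Break-even: (1 − r²)(37/36) = 1, so r = sqrt(1 − 36/37) = 0.164.

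**Repeated measures, in the SAP's covariance form.** Let V = icc + (1 − icc) × phi^|lag| over eight visits, P its post-baseline 7 × 7 block and c the covariances of baseline with those visits.
- Unadjusted, per-person variance v0 = 1/(1′P⁻¹1), and the group contrast has variance (2/20) × v0.
- With one baseline slope b = v0 × 1′P⁻¹c, the variance factor is [(v0 − b²)/v0] × 37/36.
- Example, icc 0.5 and phi 0.6: v0 = 0.700 and b = 0.620, giving (0.700 − 0.384)/0.700 × 37/36 = 0.463.

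| icc, phi | implied baseline correlation, first to last post-baseline visit | unadjusted detectable effect | variance factor | adjusted detectable effect |
|---|---|---|---|---|
| 0.3, 0.3 | 0.51 to 0.30 | 0.620 | 0.758 | 0.540 |
| 0.3, 0.6 | 0.72 to 0.32 | 0.692 | 0.640 | 0.554 |
| 0.5, 0.3 | 0.65 to 0.50 | 0.715 | 0.551 | 0.531 |
| 0.5, 0.6 | 0.80 to 0.51 | 0.761 | 0.463 | 0.518 |

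A simulation of 20,000 trials per setting, with the covariance known, gave variance ratios of 0.76, 0.65, 0.56 and 0.47, and mean error 0.00 for both estimators.

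**Weaker baselines.** These settings let baseline correlate with follow-up as strongly as follow-up visits correlate with one another. That may be optimistic. The interview's diagnostic threshold is "endorsement of three or more of the eight criterion symptoms" rated 2, so the entry total is at least 3 × 2 = 6 of 16, and the narrowed range may lower r. Holding the post-baseline structure and replacing c by one constant correlation gives factors of 0.83-0.90 at 0.3, 0.94-0.97 at 0.2 and 1.028 at 0.

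**Baseline as a response row.** If week 0 were instead placed among the responses under additive time, the single group coefficient would average in a visit with no expected effect. The weight on post-baseline visits is then 0.839 (phi 0.3) or 0.773 (phi 0.6).

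**The case against.** The strongest reply is that silence is not exclusion. The SAP is a short past-tense summary with no model equation, and a baseline term may have been fitted but not mentioned. That stands: the finding concerns the plan as written, and the loss occurred only if the fitted model matches the text.

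Second, the documents available name no primary outcome measure. The main hypothesis speaks only of symptomatic improvement. If the main test is the CGI-I or a response category, the variance figures above do not carry over. That also stands, so the bearing on the primary comparison is unknown.

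Third, the 24-54% figure rests on assumed correlations, equal spacing, no dropout and a visit count taken from a payment clause. The Assessment Instruments section gives no visit schedule, so baseline values for scales other than the interview are inferred. The early dose steps and the week 1 visit make equal spacing unlikely. This limits how firmly any one figure can be quoted, but the direction survives. A schedule with early weekly visits still shows a gain, and the risk is lopsided: about 3% of variance lost if baseline is uninformative, against 23% (r = 0.5) or 48% (r = 0.7) gained at a single visit.

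Last, the unadjusted comparison is valid. Agreed; the 11% imbalance figure is context and does not show a defect.

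**Conclusion.** The concern holds. As written, the model for quantitative outcomes has no baseline term, and nothing in the protocol text available adds one, although the interview total is scored before treatment.

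The cost is precision, not bias, and the documents cannot fix its size. Over the ranges assumed, adjustment runs from a variance increase of about 3% (zero correlation) to a reduction of about 54% (SAP structure, icc 0.5, phi 0.6). A flat correlation of 0.2 gives a 3-6% reduction. For a single visit at r = 0.5 the detectable effect falls from 0.91 to 0.80 SD, worth about 12 more patients (51.9 − 40).

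This is a change that should be made, held with medium confidence because r and the model actually fitted are unknown.

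**What to change.** - State which quantitative outcomes have a baseline measurement. For each, model the post-baseline values with that outcome's own baseline as a fixed covariate. A constrained-baseline model with a post-baseline group effect is an alternative (variance factors 0.40-0.74 in the four settings above).
- Do not add baseline to the response rows while time is only additive, since the group coefficient would recover about 77-84% of a constant effect. The SAP's reference to post-randomization values suggests this was not done, but the plan should say so.
- For the CGI-I, which already rates improvement and has no baseline of its own, adjusting for the baseline interview total is optional.
- In the logistic models, note that a baseline-adjusted odds ratio is a conditional quantity.
- If baseline was in fact used, one sentence saying how settles the point. If it was not and the analysis is finished, report the adjusted model beside the existing one, labelled as added.

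The cost is one covariate and one degree of freedom per quantitative model, with no extra patients or procedures for the interview total. If baseline proves uninformative, about 3% of variance is lost. An adjusted result added after the analysis is post hoc and cannot replace a prespecified test.
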